Official Title: Does an occupational therapy program enhance mental health outcomes for veterans who scuba dive

NCT Number: NCT03928392

Document Date: 10/14/2018

Study Protocol and Statistical Analysis Plan

METHODS

Study Design

For this study, we will be using a quasi-experimental design to compare the effectiveness of two groups: occupational therapy in combination with SCUBA diving in comparison to SCUBA diving alone. Data will be collected through semi-structured interviews and standardized assessments to assess the impact on psychosocial skills and occupational engagement.

Inclusion/Exclusion Criteria

SCUBA diver veterans who have participated in the WAVES Project for at least 3 months and have completed 3 open water dives. Participants must be proficient in written and verbal English. Veterans must be between 18-95 years of age.

Recruitment

Recruitment Method Info

We will recruit up to 15 participants in the control and experimental group for a total of 30 veterans from the WAVES Project facility. Purposeful and snowballing sampling methods will be applied to recruit participants via flyer. The flyer will be sent via email to the director of the WAVES project. The director will then forward the electronic flyer to their members via email or Facebook. Additionally, a meeting will be scheduled at the WAVES Project facility where the researchers will reach out to the veterans via a verbal recruitment script (see Appendix B) and a physical flyer (Appendix A). Those who are interested in participating will contact the researchers via email or phone and will be scheduled to

attend the first group meeting. At the group meeting the research project will be overviewed and the informed consent form will be provided.

Instruments & Data Collection

This study will include the following instruments: Intake Focus Group (Appendix D), Demographic Questionnaire (Appendix E), COPM (Appendix F), PCL-5 (Appendix G), DASS-21 (Appendix H), Discharge Focus Group (Appendix I) and Follow-Up Phone Script (Appendix J).

A Intake Focus Group consists of four sections and will be used to identify participants' experiences with SCUBA diving, impact of negative emotions on daily life and coping strategies. Focus groups will be held with those in the experimental group and control group separately..

The demographic questionnaire will obtain information about participants' age, gender, ethnicity, marital status, study and work commitments.

The Canadian Occupational Performance Measure (COPM) is “an individualized outcome measure designed to assess clients’ perception of their occupational performance and satisfaction with that performance” (Donnelly, O’Neill, Bauer, & Letts, 2017). A systematic review (Parker & Sykes, 2006) found that this assessment allows clients to identify personal goals they would like to work on throughout their time in occupational therapy (Donnelly, O’Neill, Bauer, & Letts, 2017). It has also been used in research studies to measure change in perceived performance and satisfaction with performance (Plach, Sells, 2013).

The PTSD Checklist for DSM-5 (PCL-5) assesses the 20 DSM-5 symptoms of PTSD through a 20-item self-report measure. There are several purposes of the PCL-5, including: “monitoring symptom change during and after treatment, screening individuals for PTSD, and making a provisional PTSD diagnosis.” In the PCL-5, individuals are presented with a list of problems people may have as a result of

a stressful situation. Individuals are asked to indicate how much they have been bothered by this problem in the past month. Problems can be rated as “not at all, a little bit, moderately, quite a bit, or extremely” (Weathers et al., 2013). The PCL-5 demonstrates sound psychometric properties according to Wortmann et al. (2016).

The Depression Anxiety and Stress Scales (DASS) is a screening tool to assess symptoms of depression, anxiety, and stress in community settings (Tran, Tran, & Fisher, 2013). The DASS-21 asks 21 questions and is comprised of three subscales: The Depression sub-scale which measures hopelessness, low self-esteem, and low positive affect; the Anxiety scale which assesses autonomic arousal, musculoskeletal symptoms, situational anxiety and subjective experience of anxious arousal; and the Stress scale which assesses tension, agitation, and negative affect (Tran, Tran, & Fisher, 2013). The DASS-21 will also be used as a quantitative outcome measure pre and post-test to measure changes in mental health.

Discharge focus groups will be used to identify coping strategies after participating in occupational therapy intervention in combination with SCUBA or SCUBA diving alone. Therefore, individual focus groups will be held for the experimental and control groups. Qualitative information will provide in depth information about participants’ experiences with SCUBA diving and occupational therapy, and the impact on mental health and daily life.

Follow-up phone interviews will be held individually with each participant in the experimental group. The interview will consist of six questions and be used as a qualitative outcome measure to explore the effects of occupational therapy in combination with SCUBA diving and its impact on participants’ mental health and daily life.

Informed Consent Process

Veterans interested in the study will be scheduled to attend a group meeting. At the meeting, the research study will be briefly described and the informed consent document will be provided and reviewed. Those who are interested in participating will sign the consent form prior to completing pre-assessments. Those who are interested in participating will sign the consent form prior to completing pre-assessments.

Procedures

After receiving IRB approval, we will:

1. Email the flyer (see Appendix A) to the WAVES director and ask the director to send the flyer to members of the WAVES.
2. Schedule recruitment opportunities to present the flyer (see Appendix A) and verbal recruitment script (see Appendix B) at end of a *WAVES* session to recruit up to 30 *WAVES* veterans with mental health conditions. Provide signup sheet to sign up if interested.
3. Hand out flyers (with contact information i.e. phone number and email) to participants of *WAVES*.
4. Individuals interested may contact the research team via email and phone to sign up for the study.
5. Interested individuals will arrive at the group meeting at the scheduled time (the group meeting will last 1 ½ hours).
6. At the group meeting, provide a brief overview of the study and informed consent document, approximately 5 minutes.
7. Obtain written informed consent to participate in study, approximately 10 minutes.
8. Randomly assign participants into one of two groups before pre-testing: Experimental group or control group, approximately 10 minutes.

9. Provide further explanation about SCUBA, occupational therapy and the research program, approximately 10 minutes.
10. For pre-test questionnaires, have participants complete the COPM (Appendix F), PCL-5 (Appendix G), and DASS-21 (Appendix H). approximately 25 minutes.
11. The group will then split and focus groups (see Appendix K) will be held for the experimental and control groups, approximately 25 minutes.
12. Conclude the meeting and review the upcoming schedule (as described in the following), approximately 5 minutes.
13. Participants in the **experimental group** will complete 3-week OT program for 1.5 hours each week. After 4 weeks total, a follow-up phone call will be given with general questions regarding experience with OT and SCUBA diving.

(See Appendix K for more details of research program)

Week 1	Week 2	Week 3	Week 4	Week 8
Informed consent Pre-test assessments Focus Group (audio will be recorded and transcribed)	OT Program Orientation Mindfulness strategies Journaling activity	OT Program Social community reflection Focus group to reflect on week 1 (audio will be recorded and transcribed) (See focus group questions in Appendix K)	OT Program Social community reflection Focus group to reflect on week 2 (audio will be recorded and transcribed) (See focus group questions in Appendix K)	Follow-up phone call after 4 weeks (audio recorded and transcribed) Discharge focus

		
Journaling activity
 
Trust-building activity
 
Total time: 1.5 hours
	
group (audio will be recorded and transcribed)
 
Journaling activity
 
Post-test assessments
 
Total time: 1.5 hours
	
--	--	---	---	--

14. Participants in **control group** will continue SCUBA diving without OT. They will participate in a discharge focus group discussion and complete post-test assessments. However, they will not receive a follow up phone call.

Week 1	Week 2	Week 3	Week 4
Informed consent	SCUBA dive without OT	SCUBA dive without OT	SCUBA dive without OT
Pre-test assessments			Post-test assessments

Focus Group (audio will be recorded and transcribed)
 
Total time: 1.5 hours
			
Discharge focus group (audio will be recorded and transcribed)
 
Total time: 1.5 hours

---	--	--	---

15. For post-test, have participants complete the COPM (Appendix F), PCL-5 (Appendix G), and DASS-21 (Appendix H).
16. The discharge focus group will be completed for both the experimental and control groups during week 4.
17. Complete field notes.
18. Transcribe focus groups within two weeks.
19. Complete follow up phone call after 4 weeks, for experimental group only, following the follow-up phone script (Appendix J).
20. Upload interviews to DeDoose for qualitative data analysis
21. Utilize SPSS to analyze quantitative data from COPM, PCL-5, and DASS-21

Risk and Injury

Breach of Confidentiality

- Pseudonyms will be used to identify participants; a master list will document each participant's pseudonym. The master list will be stored separately to all data collected. All interviews will be transcribed by using headphones to ensure others will not hear the data. Data collected from focus groups, interviews and questionnaires will be stored electronically and in hard copy. Data

in hard copy will be kept in a locked file and electronic data will be password protected. Within two weeks of recording and following audit for correctness of transcriptions, the audio recordings will be destroyed.

Discomfort/vulnerability disclosing personal information

Some focus group or interview questions may be upsetting or uncomfortable for participants. Participants will be informed that they do not need to share any information that they wish not to with the group or that makes them uncomfortable. If the participants experience emotional discomfort at any time throughout the duration of the study, they may refuse to answer the question or withdraw from the study at any time.

Data Management Including Labeling & Storage Data

Subject/Data Confidentiality

- To protect the participants' identity, the researchers will assign pseudonyms and create a master list. The master list containing participant's legal names will be available only to the researchers. Electronic data will be stored in secure files on a password protected school shared server. The master list will be stored separately to collected data.
- All hard copy data will be stored in a locked file until the study is completed, in a secure office at Loma Linda University.
- Upon completion of the data collection, the data will be stored for a minimum of three years in a locked file in the school of Allied Health Professions at Loma Linda University. Three years post research data will be destroyed.

Data Analysis

- Qualitative data will include focus groups and interviews and these will be transcribed verbatim. Transcripts will be coded individually, and then together as a group. A codebook will be created and then categorized to organize emerging themes.
- Once the quantitative data is completed, it will be uploaded into a database in SPSS for analysis. Demographic information will be analyzed using descriptive analysis. Changes in COPM, PCL-5, and DASS-21 scores will be tested using paired samples t-tests. Further, differences between groups will be analyzed using independent samples t-tests.

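### Procedures step 2 speaks of veterans with mental health conditions but the eligibility criteria name none; reconcile the wording, take the pre-test before assignment, and adjust the group comparison for it

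*Combined protocol and SAP*

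**What the plan says.** All references are to the combined protocol and SAP.

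- **Inclusion/Exclusion Criteria:** "SCUBA diver veterans who have participated in the WAVES Project for at least 3 months and have completed 3 open water dives", plus proficiency in English and age 18-95. No diagnosis, condition or symptom threshold appears.
- **Official title:** it asks about "mental health outcomes for veterans who scuba dive", again with no condition.
- **Recruitment Method Info:** up to 15 per group, 30 in total, from the WAVES facility. "Purposeful and snowballing sampling methods will be applied to recruit participants via flyer"; the characteristic that makes the sampling purposeful is not given.
- **Procedures, step 2:** the people to be recruited are WAVES "veterans with mental health conditions".
- **Procedures, step 4:** "Individuals interested may contact the research team via email and phone to sign up for the study".
- **Procedures, step 8:** "Randomly assign participants into one of two groups before pre-testing".
- **Procedures, step 10:** "For pre-test questionnaires, have participants complete the COPM (Appendix F), PCL-5 (Appendix G), and DASS-21 (Appendix H"). No score is given a role in entry.
- **Data Analysis:** changes on the three measures are tested with paired t-tests and group differences with independent samples t-tests. The text does not say whether the group test uses post-test or change scores, and it states no adjustment for the pre-test.

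**The concern.** Step 2 names a narrower group than the criteria do. Followed literally, the criteria let in a diver with few or no symptoms. PCL-5 and DASS-21 score symptoms, so such a diver has little room to improve on them. COPM rates self-chosen goals and is not directly affected. The plan should say plainly whether its conclusions concern WAVES divers in general or those with a mental health condition.

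Two features of the plan matter more if baseline scores vary widely. First, the pre-test is self-reported and is completed after participants learn their group, so the answers may be coloured by that knowledge. Second, the group comparison makes no stated use of the pre-test as a covariate, although every participant supplies one. In arms of at most 15, precision is scarce.

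**Working it through.** **The population wording, side by side**

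| Place | Population | Condition named? |
|---|---|---|
| Official title | veterans who dive | no |
| Inclusion/Exclusion Criteria | WAVES divers, 3 months, 3 dives, English, 18-95 | no |
| Recruitment Method Info | 30 veterans from WAVES | no |
| Procedures, steps 1 and 3 | flyer to WAVES members and participants | no |
| Procedures, step 2 | WAVES veterans with a mental health condition | yes |

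Steps 4 to 8 are sign-up, arrival, overview, consent and assignment. None describes a check for a condition, and none describes a check of the other criteria either. The demographic questionnaire, as described under Instruments & Data Collection, lists no mental health item. One phrase therefore stands apart from the rest.

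**The plan's own figures**

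- Sample size: 15 + 15 = 30, as stated.
- Meeting time: step 5 says "the group meeting will last 1 ½ hours". Steps 6 to 12 take 5 + 10 + 10 + 10 + 25 + 25 + 5 = 90 minutes, which agrees.
- With step 10 moved ahead of step 8, the order is 6, 7, 10, 8, 9, 11, 12: 5 + 10 + 25 + 10 + 10 + 25 + 5 = 90 minutes, unchanged.

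**What adjustment is worth**

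Inputs: n = 15 per arm (the stated maximum). The pre-post correlation r is not in the documents, so 0.3, 0.5 and 0.7 are assumed. Also assumed are random assignment in equal numbers, normal scores, and the same SD (σ) before and after.

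Variance of the estimated group difference:

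- Post-test t-test: 2σ²/n
- Change-score t-test: (2σ²/n) × 2(1 − r)
- ANCOVA: (2σ²/n) × (1 − r²) × (1 + 1/(2n − 4)), where 1 + 1/26 = 1.0385

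| r | ANCOVA / post-test = (1 − r²) × 1.0385 | 2(1 − r) | ANCOVA / change score |
|---|---|---|---|
| 0.3 | 0.91 × 1.0385 = 0.945 | 1.4 | 0.675 |
| 0.5 | 0.75 × 1.0385 = 0.779 | 1.0 | 0.779 |
| 0.7 | 0.51 × 1.0385 = 0.530 | 0.6 | 0.883 |

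At r = 0.5 the gain is like having 15 / 0.779 ≈ 19 per arm under either t-test.

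Break-even against the post-test t-test: (1 − r²) × 27/26 = 1, so r² = 1/27 and r = 0.192. Below that, ANCOVA loses slightly.

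None of these ratios depends on whether a mental health condition is required for entry. They measure the gain from adjustment, not the effect of the wording conflict.

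**The case against.** The strongest reply is that nothing substantive is in conflict. Step 2 is a recruitment instruction, not a definition of the population. The title, the criteria, the Recruitment section and steps 1 and 3 all point to WAVES divers without restriction. The phrase may simply be how the authors describe WAVES members. The flyer and recruitment script (Appendices A and B) are not in the supplied text and may state the target group. This largely stands. It rules out four stronger readings that a reader might infer:

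- **The plan defines two different populations.** The documents do not describe WAVES membership, so the two descriptions may coincide.
- **Nobody is checked for a condition.** All that can be said is that the numbered steps describe no check.
- **The study loses a known amount of power.** There are no baseline scores and no share of low-symptom divers in the documents, so any dilution cannot be sized.
- **The unadjusted t-test is invalid because the arms may differ at baseline.** Under random assignment, chance imbalance is already allowed for in the test's error rate. With 15 per arm, a gap above 0.5 SD on a given scale has a chance of about 17% (standard error √(2/15) = 0.365; 0.5 / 0.365 = 1.37). That figure depends on the arm size and would be essentially the same if every participant had a diagnosis.

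What survives is that step 2 and the criteria do not match on their face, and a flyer naming a condition would not change the criteria. The two analytic improvements stand on their own merits, whichever way the wording is settled.

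**Conclusion.** The concern holds as a modest but worthwhile correction. One phrase in step 2 is not matched by the eligibility criteria, and the supplied text cannot settle which is meant. The criteria as written admit divers with few or no symptoms. No loss of power or validity is attributed to this.

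The measurable gain comes from adjusting for the pre-test: a variance 5% to 47% below that of a post-test t-test, or 12% to 32% below that of a change-score t-test, for r between 0.3 and 0.7. The benefit of taking the pre-test before assignment is not quantified. It removes one route by which knowledge of the arm could influence baseline answers.

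The figures rest on 15 per arm and on random assignment as in step 8. Study Design calls the study quasi-experimental, and step 8 gives neither a method nor a ratio, so random assignment in equal numbers is itself an assumption here.

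**What to change.** 1. **Reconcile step 2 with the criteria.** Either of two routes will do.
   - *All WAVES divers are eligible:* delete the phrase, state conclusions for WAVES divers, and report baseline PCL-5 and DASS-21 by arm. Cost: one deletion and one table from data already collected.
   - *A mental health condition is required:* add it to the criteria and check it before step 8. Cost: one sentence and one question, possibly slower recruitment. Asked at sign-up, the question precedes consent and the ethics board would need to accept that. Asked after consent, it adds a few minutes to a meeting that is already full and may turn away people who have signed.
2. **Replace the between-group t-test with ANCOVA** for COPM, PCL-5 and DASS-21 alike: post-test score by group, adjusted for the pre-test score on the same scale. Cost: one degree of freedom per model (27 instead of 28 with 30 participants) and a slight loss against the post-test t-test if r is below about 0.19. The planned software and data suffice. This improves precision; it does not remove floor effects or settle the wording.
3. **Complete step 10 before step 8.** Cost: a change of order only, with the timed total still 90 minutes.

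### Participants are assigned at random before they complete the self-rated pre-tests, and nothing says the arm is withheld, so the baseline is open to avoidable bias

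*Combined protocol and SAP*

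**What the plan says.** The Procedures section sets out one group meeting as a timed sequence. After written consent (step 7), step 8 is "Randomly assign participants into one of two groups before pre-testing: Experimental group or control group, approximately 10 minutes". Step 9 is "Provide further explanation about SCUBA, occupational therapy and the research program, approximately 10 minutes". Step 10 is the baseline: "For pre-test questionnaires, have participants complete the COPM (Appendix F), PCL-5 (Appendix G), and DASS-21 (Appendix H). approximately 25 minutes". Step 11 is the first step that cannot be carried out without revealing the arm: "The group will then split and focus groups (see Appendix K) will be held for the experimental and control groups, approximately 25 minutes".

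Instruments & Data Collection describes the PCL-5 as self-report and the COPM as a measure of the client's own perception. Step 10 has the participants themselves complete the DASS-21. For the PCL-5, "Individuals are asked to indicate how much they have been bothered by this problem in the past month".

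Under Data Analysis, "Changes in COPM, PCL-5, and DASS-21 scores will be tested using paired samples t-tests", and "differences between groups will be analyzed using independent samples t-tests". The plan does not say whether the between-group tests use change scores or post-test scores. The supplied text contains no rule that keeps the arm from participants until the questionnaires are done.

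**The concern.** A baseline measure should not be able to respond to the allocation. Here all three instruments depend on the participant's own judgement, and assignment is deliberately placed ahead of them. A participant who knows the result may rate the pre-test differently. Someone assigned to occupational therapy might report more difficulty, which would later look like improvement and favour the programme. Someone disappointed to be in the control arm might do the same, which would work against it. The COPM may be the most exposed, because the plan describes it as a way to identify goals for occupational therapy. Knowing whether one will receive that therapy could alter which goals are named as well as how they are rated. That last point is an inference from the plan's description.

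The baseline enters the paired tests directly. A shift at baseline that later fades is arithmetically the same as a change over the study, and no later analysis can separate the two.

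**Working it through.** **1. Is the order a real sequence?** Steps 6 to 12 take 5 + 10 + 10 + 10 + 25 + 25 + 5 = 90 minutes, which equals the stated meeting length of 1 ½ hours. The steps fill the meeting exactly, which supports reading them as a running order. The wording of step 8 itself also puts assignment ahead of the pre-tests.

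**2. When is the arm known?** It must be known at step 11. It may be known from step 8, a 10-minute item in a meeting the participants attend, and nothing says the result is held back. Disclosure before step 10 is the likely reading, but it is not stated.

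**3. Which planned tests carry a baseline shift?** Let the shift be δ (in SD units, in one arm) and let p be the share still present at week 4.

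- Paired test in the shifted arm: carries δ(1 − p).
- Independent test on change scores: carries δ(1 − p).
- Independent test on post-test scores: does not carry the part that has faded.

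**4. Illustration of size.** The documents give no shift, correlation, SD or significance level. Assumed: two-sided alpha 0.05, equal SDs, pre-post correlation r = 0.6, no true change in either arm, shift in one arm only. The 15 per arm is the plan's maximum.

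- SD of change = √(2(1 − r)) = √0.8 = 0.894 SD.
- Independent test on change: noncentrality δ(1 − p) / (0.894 × √(2/n)), df = 2n − 2.
- Paired test: noncentrality δ(1 − p) × √n / 0.894, df = n − 1.
- Example, δ = 0.3, p = 0, n = 15: independent 0.3 / (0.894 × 0.365) = 0.92, df 28, rejection 14.4%. Paired 0.3 × 3.873 / 0.894 = 1.30, df 14, rejection 22.8%.

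Rejection rates, nominal 5%:

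| n per arm | Share persisting | Test | δ = 0.1 | 0.2 | 0.3 | 0.5 |
|---|---|---|---|---|---|---|
| 15 | none | independent, change | 6.0% | 9.1% | 14.4% | 31.5% |
| 15 | none | paired, shifted arm | 6.9% | 12.7% | 22.8% | 52.2% |
| 15 | half | independent, change | 5.3% | 6.0% | 7.3% | 11.5% |
| 15 | half | paired, shifted arm | 5.5% | 6.9% | 9.3% | 17.2% |
| 15 | all | either | 5.0% | 5.0% | 5.0% | 5.0% |
| 10 | none | independent, change | 5.6% | 7.6% | 11.0% | 22.0% |
| 10 | none | paired, shifted arm | 6.2% | 9.7% | 15.8% | 35.2% |

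**5. Sensitivity to the correlation** (δ = 0.3, n = 15, r from 0.5 to 0.7). With none persisting, independent 12.5% to 17.6% and paired 19.2% to 28.7%. With half persisting, 6.8% to 8.1% and 8.4% to 10.8%.

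**6. Simulation check** (δ = 0.3, none persisting, n = 15, r = 0.6). Independent on change 14.3%; paired 22.3% in 60,000 trials and 22.8% in 400,000; independent on post-test scores 4.9%, so the faded shift does not reach that comparison.

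**The case against.** The strongest reply is that the mechanism is conditional. The plan says participants are assigned at step 8, not that they are told, and the arm need not be visible until the split after the questionnaires. The appendices and the consent form are not in the supplied text, so a disclosure rule there cannot be excluded. This stands, and it is why the point is worded as exposure to bias.

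Second, every quantity in the illustration is assumed. The large rejection rates need a sizeable shift, in one arm, that arises within minutes and is gone by week 4. At 0.1 to 0.2 SD with half persisting, the rates are about 5% to 7%. Persistence is plausible, because the post-tests are also rated by people who know their arm. The recall frame of the PCL-5 may also limit the shift on that scale. This stands too: the table shows how the exposure behaves, not how large it is in this trial.

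Third, the between-group tests may turn out to use post-test scores, leaving only the paired tests exposed, and within-arm tests cannot isolate the effect of occupational therapy in any case. That narrows the consequence, but the plan has not made that choice and the paired tests are planned.

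Fourth, expectation effects on the open-label post-tests remain whatever the order. True, but an unavoidable weakness at week 4 is no reason to accept an avoidable one at baseline.

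Finally, hearing about occupational therapy before the COPM may be intended. The explanation at step 9 is a lesser matter in any case: both arms appear to hear it, and the study is already outlined before consent at step 6. The essential fix does not require moving it.

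**Conclusion.** The point holds and should be fixed. The stated order puts random assignment ahead of a participant-rated baseline, without any statement that the arm is withheld, and the planned paired t-tests use that baseline directly. Between-group tests are exposed only if they use change scores. The direction is unknown and the size cannot be derived from the documents. Under the assumptions above, the false-positive rate ranges from the nominal 5%, when the shift persists in full, to 32% (independent, on change) or 52% (paired) for a 0.5 SD shift in one arm that fades completely. Confidence is medium, because disclosure at step 8 is inferred. The case does not rest on any one value in the table: the exposure is avoidable, and nothing in the documents gives a reason for assigning first.

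**What to change.** In step 8, change the timing of assignment to after pre-testing, and reorder the meeting:

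1. Overview (step 6) and consent (step 7).
2. COPM, PCL-5 and DASS-21 completed and the forms collected (step 10).
3. Random assignment (step 8).
4. Explanation of the programme (step 9).
5. Split for focus groups (step 11) and close (step 12).

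The essential change is that the pre-tests are in hand before assignment is made or revealed. Moving step 9 is secondary; if the team wants participants to hear about occupational therapy before the COPM, it can stay ahead of the pre-tests. If the assignment has to be drawn earlier, add one sentence saying that it is not revealed until the pre-test forms are collected.

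The cost is nil beyond reordering: 5 + 10 + 25 + 10 + 10 + 25 + 5 = 90 minutes, the same meeting with no added participants or burden. The change has to come before baseline data are collected, since a baseline taken after disclosure cannot be recovered. It does not remove expectation effects on the week 4 ratings.

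### The fuller explanation of the OT programme and the schedule review come after consent and random assignment, an avoidable risk of unequal post-assignment loss that the analysis plan does not cover

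*Combined protocol and SAP*

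**What the plan says.** The Procedures section of the combined protocol and SAP sets out the first meeting as a timed list:

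- Step 6: "At the group meeting, provide a brief overview of the study and informed consent document, approximately 5 minutes".
- Step 7: "Obtain written informed consent to participate in study, approximately 10 minutes".
- Step 8: "Randomly assign participants into one of two groups before pre-testing: Experimental group or control group, approximately 10 minutes".
- Step 9: "Provide further explanation about SCUBA, occupational therapy and the research program, approximately 10 minutes".
- Step 10: the pre-test questionnaires (25 minutes).
- Step 11: separate focus groups by arm (25 minutes).
- Step 12: "Conclude the meeting and review the upcoming schedule (as described in the following), approximately 5 minutes".

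The Informed Consent Process section agrees with this order: the study is described briefly and the form is reviewed before anyone signs. The Recruitment section adds an earlier flyer and verbal script.

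After the meeting, steps 13 and 14 give the experimental arm three weekly OT sessions of 1.5 hours and a later phone call. Controls go on diving and attend a week 4 post-test and discharge focus group, with no call. Both arms have audio-recorded focus groups.

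Under Risk and Injury, participants may withdraw at any time. Data Analysis plans paired and independent samples t-tests. It names no analysis population, missing-data method or replacement rule.

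**The concern.** The plan itself treats a further explanation and a schedule review as necessary, yet places both after people have signed and been assigned. Someone who finds the content unwelcome or the dates unworkable at that point is already a randomised participant who knows their arm. If they leave, the loss depends on the arm they were given. A refusal before assignment would not.

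The two arms ask for different amounts of time, so a reason to leave that is tied to time or programme content would weigh more on the OT arm. Nothing under Inclusion/Exclusion Criteria asks whether a person can attend the sessions.

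Two things are at stake. The comparison could become one of completers, whose arms no longer match as randomisation intended. Fewer of the up to 15 people in the OT arm might also receive the programme.

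**Working it through.** **1. Meeting length.** Steps 6 to 12: 5 + 10 + 10 + 10 + 25 + 25 + 5 = 90 minutes, which reproduces the stated 1½ hours.

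**2. Current and proposed order.** This assumes that all 5 minutes of step 12 move with the schedule review.

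| | Current (6, 7, 8, 9, 10, 11, 12) | Proposed (6, 9, 12, 7, 8, 10, 11) |
|---|---|---|
| Consent signing starts | minute 5 | minute 5 + 10 + 5 = 20 |
| Assignment starts | minute 5 + 10 = 15 | minute 20 + 10 = 30 |
| Explanation and schedule time after assignment | 10 + 5 = 15 min | 0 min |
| Total | 90 min | 90 min |

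**3. Scheduled study contact by arm, diving excluded.** As the schedule tables read, the OT arm's post-test and discharge focus group fall inside the week 4 OT session.

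- OT arm: 1.5 + 3 × 1.5 = 6.0 h, plus a call.
- Control arm: 1.5 + 1.5 = 3.0 h.

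**4. What happens to a leaver in the analysis.**

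- Someone who leaves at step 9 has no pre-test (step 10) and cannot enter a paired t-test.
- Someone who leaves after step 12 has a pre-test but no post-test, and is also lost to the paired test.
- An OT participant who misses the week 4 session also misses the post-test unless it is arranged separately.

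**5. Illustration of size.** Every input here is an assumption; the plan states no alpha, effect size, SD or dropout. Suppose k of 15 leave the OT arm and none leave the control arm.

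Power uses the noncentral t distribution at two-sided alpha 0.05, with df = n₁ + n₂ − 2 and noncentrality d / √(1/n₁ + 1/n₂). For 12 v 15 at d = 0.8, the noncentrality is 0.8 / √(1/12 + 1/15) = 0.8 / 0.387 = 2.07.

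Completer-only bias is (k/15) × g, where g is the leaver–stayer difference in outcome, in SD.

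| k | Power, d = 0.5 | Power, d = 0.8 | Power, d = 1.0 | Bias for g = 0.25 to 1.0 SD |
|---|---|---|---|---|
| 0 | 26.2% | 56.2% | 75.3% | 0 |
| 1 | 25.5% | 54.6% | 73.7% | 0.02 to 0.07 SD |
| 3 | 23.7% | 51.0% | 69.9% | 0.05 to 0.20 SD |
| 5 | 21.7% | 46.7% | 65.0% | 0.08 to 0.33 SD |

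One leaver matters little. Several leavers who differ from the stayers could matter in a trial this small.

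**The case against.** The strongest reply is that participants are not uninformed when they sign. They may have had a flyer, a verbal script and contact with the researchers. At the meeting they get the overview, a consent form that is provided and reviewed, and 10 minutes for consent. Step 9 is described as further explanation, which implies some came before. If the flyer, script or consent form already lists the sessions, dates and recordings, little is left to discover after assignment. This stands as a limit on the point. Those texts are not available, so neither their adequacy nor any gap in them can be shown.

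Four stronger readings are tempting but unsupported:

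- **That people will leave, and unequally.** The documents give no withdrawal data or expectation. Controls might also leave on learning that they will not receive OT.
- **That most of the explanation comes after assignment.** Setting the 15 later minutes against the 5 minutes of step 6 suggests this. The split is even if step 7 counts as information (5 + 10 = 15 before, 15 after), and recruitment contact is not timed at all. Part of step 9 concerns SCUBA, which entrants already know.
- **That the burden is one-sided.** Controls have recorded focus groups in weeks 1 and 4 and a post-test visit. Reluctance to be recorded applies to both arms.
- **That earlier decliners would be replaced.** Recruitment is for up to 15 per arm from one facility, with no replacement rule.

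It is also fair to say that reordering the agenda does not supply a missing-data rule. It removes one avoidable cause of loss but does not deal with the others.

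**Conclusion.** The point holds as an avoidable risk of unknown size. The order of steps is explicit, the OT arm has about twice the scheduled contact (6.0 h v 3.0 h) plus a call, and the analysis has no rule for people who leave after assignment. Some participants may learn the full content or dates only after assignment and may then withdraw or not attend, more likely in the OT arm.

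How much this matters depends on what the unseen flyer, script and consent form say, and on how many people would react to the later detail. The power and bias figures show only what would follow from assumed losses; they are not forecasts. The point also takes step 8 at its word that assignment is random, although Study Design calls the trial quasi-experimental. This is a cheap improvement to the conduct of the meeting. It does not show that the consent process is inadequate.

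**What to change.** Run the meeting in the order 6, 9, schedule review from 12, 7, 8, 10, 11. Before anyone signs, state the session dates for both arms and which sessions are recorded. Before assignment, ask each person whether they could attend either arm's schedule, and record the answer. If a negative answer is to exclude someone, Inclusion/Exclusion Criteria should say so.

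The cost is nil in meeting time (still 90 minutes) and staff. The downside is that a few people may decline before assignment who would otherwise have been enrolled. This slightly narrows the sample and may leave the arms below 15.

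Separately, Data Analysis needs a sentence on how people who leave after assignment are handled, since reordering does not settle that.
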